### 3.2 Exclusion Criteria

Subjects are excluded from the study if any of the following criteria are met:

1. Medical instability limiting ability to travel to the investigative center.
2. The presence of medical illness expected to complicate participation and/or compromise the safety of this technique, such as active infection with HIV, hepatitis B or hepatitis C, as determined by hepatitis B surface antigen screening, detection of hepatitis C antibodies, or positive result of hepatitis C PCR analysis.
3. Active infection in the area that will undergo administration
4. Evidence of systemic infection.
5. Known allergy to any of the constituents of the product.
6. Current evidence or a history of squamous cell carcinoma in the area that will undergo treatment.
7. Active drug or alcohol addiction.
8. Hypersensitivity to local anesthesia (lidocaine/prilocaine cream).
9. Receipt of chemical or biological study product for the specific treatment of RDEB in the past three months, except for KB103.

10. Specific wounds that have previously been administered investigational gene or cell therapy. Wounds previously administered KB103 are not excluded.
11. Positive pregnancy test or breast-feeding.
12. Clinically significant abnormalities as determined by the investigator.

## 4 Study Design

### 4.1 Study Overview

This study is an intrasubject comparison of KB103-administered and placebo-administered wounds. Up to three 50 cm^2 areas will be selected for entry: one or two will be selected to receive topical KB103, and one to receive topical placebo.

The primary objective of this study is to evaluate clinical efficacy through digital imaging of wounds. Secondary objectives include an evaluation of change in an Investigator's global assessment and change in patient reported outcomes.

[figure not shown]
Patients will be administered Investigation Product (IP) in two cycles. Cycle 1 starts on Day 1. Up to three 50 cm^2 areas are administered IP (one or two KB103 and one placebo) every 2 to 3 days (to correspond with bandage changes) until wound closure, or up to 3 months. IP is administered to the entire areas, on the wound(s) and on intact skin.

Following this initial dosing period, patients will enter into an observation period in which wounds are monitored at home using a phone imaging app. Upon re-opening and/or expansion of a wound in the KB103 treatment area, patients will be asked to return to clinic or will be treated at home to begin the 2nd cycle of dosing.

The 2nd cycle mimics the first. The same 50 cm^2 areas are administered IP (one or two KB103 and one placebo) every 2 to 3 days until wound closure or up to 3 months. IP is administered to the entire areas, on the wound(s) and on intact skin.

After the 2nd cycle of IP administration, patients enter a second observation period. Patients image their wounds at home using a phone app, and return to the clinic at monthly intervals.

Time to wound closure and duration of wound closure will be evaluated after both the 1st and 2nd cycles. Safety will be monitored throughout the study.

Three additional new patients age 2 and older will be enrolled under this version. Patients from this protocol will be allowed to roll over into Phase 3 study of KB103.

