## 2 Objectives

### 2.1 Primary

- 1) To assess wound closure through post-administration imaging:
  - a. Change in surface area of a KB103-administered wound relative to the same wound at baseline and the placebo administered wound
  - b. Time to wound closure of a KB103-administered wound relative to a placebo-administered wound
  - c. Duration of wound closure of a KB103-administered wound relative to a placebo-administered wound

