### 5.4.2 At-home Procedures

After the first administration of each cycle, KB103 may be administered at home by a caretaker every 2 to 3 days until wound closure, a stopping criterion is met, 3 months have elapsed, or until directed to discontinue by the Investigator.

Appendix 1 provides administration instructions. Wound closure is monitored through remote imaging.

### 5.4.3 Last Dosing Day of Cycle 1

The patient will visit the Investigative site on or near the final Cycle 1 administration day, in which the following procedures will be performed:

- Collection of blood (approximately 10 mL) for clinical laboratory tests:
  - Serum chemistry
  - Hematology
  - Viral shedding
  - HSV and COLVII autoantibodies
- Collection of urine for viral shedding
- Optional: biopsy collection from a wound area
- Wound stenciling
- Topical administration of KB103 and placebo to the target areas

## 5.5 Observation Period (OP) 1

Following Cycle 1 wound closure and/or 3 months, the patient returns home. Wound areas are imaged every 2 to 3 days at home with a phone app.

The duration of OP 1 varies. If complete wound closure is obtained during Cycle 1, OP 1 ends when the wound(s) re-open. If complete closure is not obtained during Cycle 1, OP 1 ends when the wound surface area increases relative to size of the wound at the last Cycle 1 administration.

## 5.6 Cycle 2

The patient will visit the Investigative site for the first dose of Cycle 2. Additional Cycle 2 doses can occur on-site or at-home at the discretion of the Investigator. For Cycle 2, KB103 and placebo are administered topically every 2 to 3 days to correspond with bandage changes, up to 3 months.

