## **6.5 Placebo Administration**

A wound area is selected to serve as the control at baseline. Topical placebo is administered on the days in which KB103 is administered. If KB103 is not administered to both of the KB103-selected wound areas on any dosing day, then placebo will not be administered. The dressings applied to the wound area that is administered the placebo gel mimic those applied to wound area administered KB103.

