### 10.5.3 Target Wound Area

Target wound surface area is obtained through on-site and at-home imaging of target areas. Change in area from baseline is evaluated for using a paired t-test for each KB103 target wound vs. control wound.

Time to closure and durability of closure will be assessed after each cycle of administrations.

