8.1.2 Time to Wound Closure

The time to wound closure defined as the time from the first treatment to complete wound closure ($\geq 90\%$ reduction in wound surface from baseline for 2 consecutive weeks) will be summarized by treatment and compared using analysis of variance with treatment as the fixed effect. This analysis will be performed for both Observed and LOCF imputed ITT populations

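### Cycle 2 starts when the KB103 wound itself re-opens or expands, so a Cycle 2 time-to-closure comparison with placebo is not like for like, and Cycle 1 duration needs a stated rule for where placebo closures end

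*Protocol*

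**What the plan says.** **Trigger.** Protocol 4.1 (and the synopsis) starts Cycle 2 from the KB103 area: "Upon re-opening and/or expansion of a wound in the KB103 treatment area, patients will be asked to return to clinic", or treatment begins at home. Protocol 5.5 does not name the arm. For closed wounds, "If complete wound closure is obtained during Cycle 1, OP 1 ends when the wound(s) re-open"; otherwise, "OP 1 ends when the wound surface area increases relative to size of the wound at the last Cycle 1 administration". Under Protocol 6.5 placebo has no clock of its own: "Topical placebo is administered on the days in which KB103 is administered".

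**Endpoints.** Primary objective 1c in Protocol 2.1 is "Duration of wound closure of a KB103-administered wound relative to a placebo-administered wound"; objective 1b is the same contrast for time to closure. Protocol 4.1 adds "Time to wound closure and duration of wound closure will be evaluated after both the" first and second cycles, and Protocol 10.5.3 repeats it: "Time to closure and durability of closure will be assessed after each cycle of administrations". The protocol gives no Cycle 2 time zero, no censoring rule, and no rule for a placebo wound still closed when Cycle 2 starts.

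**SAP.** There is no per-cycle analysis. In 8.1.2, "The time to wound closure defined as the time from the first treatment to complete wound closure", closure being at least a 90% reduction for two consecutive weeks. In 8.1.3, duration ends when that wound's own reduction falls below 90%. Both use analysis of variance with treatment as the fixed effect, with no censoring and no subject or cycle term. SAP 6.2 defines no new baseline for Cycle 2.

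**Images.** Footnote 4 of the Schedule of Events (Protocol Table 2) has home imaging continue throughout the study.

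**The concern.** The outcome of one arm sets the boundary between cycles for both arms. This matters in two places.

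- **Cycle 1 duration.** On the 4.1 reading, the KB103 closure that triggers Cycle 2 is seen to its re-opening by design. A placebo closure still intact on that date is not. If assessment after each cycle is taken to mean up to the start of Cycle 2, those placebo durations are shortened and nothing in the analysis of variance corrects for it.
- **Cycle 2 time to closure.** The KB103 wound is open because the rule selected it when open. The placebo wound was not selected, so some are open and some closed. A closed wound has no obvious time to closure, and the open ones are a different selection of wounds from the KB103 ones.

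Primary objectives 1b and 1c would then include a contrast whose sign depends on an unwritten rule. SAP section 1 says the study is not blinded and that the SAP was prepared after a partial analysis; SAP section 8 sets one-sided 5% tests. An unwritten rule could therefore be settled with results in view.

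**Working it through.** The plan states no sample size, effect size or bias figure for these endpoints, so there is nothing of its own to reproduce. The check is what each counting rule gives when KB103 has no effect.

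**Assumptions (none is in the documents).** Both wounds follow the same open/closed process, starting open, and Cycle 2 starts when the KB103 wound re-opens. Mean time open is 10 to 60 days and mean time closed 30 to 90 days. Gamma shape is 0.5 to 2 (1 is exponential). Variation between subjects or between wounds (frailty) has CV 0 to 1.0. There is one KB103 area, and KB103 wounds not closed within 90 days are left out. I ran 11 scenarios of 6,000 subjects and used an unpaired two-group test, one-sided 5%.

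**Step 1: Cycle 1 duration, simplest case.** If both wounds close on the same day with independent exponential durations of mean m, the placebo duration cut at KB103 re-opening has mean E[min(T_P, T_K)] = m/2, a ratio of 0.50. For Weibull shape 2 the ratio is 2^(-1/2) = 0.71.

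**Step 2: Cycle 1 duration, closing dates differing.** Mean days closed in selected scenarios:

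| Mean open/closed (days), shape, frailty | KB103 | Placebo cut at Cycle 2 start | Ratio | Placebo to own re-opening |
|---|---|---|---|---|
| 30/60, 1, none | 58.6 | 34.6 | 0.59 | 59.7 |
| 30/30, 1, none | 29.8 | 19.3 | 0.65 | 29.6 |
| 30/60, 2, none | 59.7 | 39.9 | 0.67 | 60.9 |
| 30/60, 1, subject and wound CV 0.7 | 62.4 | 30.4 | 0.49 | 61.8 |

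Over all 11 scenarios:

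- 30% to 47% of placebo closures are cut, and the ratio is 0.49 to 0.67.
- With the cut, one-sided rejection in favour of KB103 is 3.5% to 8.7% with 3 subjects and 6.7% to 33% with 12.
- With each closure followed to its own re-opening, rejection with 12 subjects is 2.9% to 6.1%.
- Keeping only placebo closures completed before Cycle 2 does not help (31.5 v 58.6 days in the first row).
- Censoring at Cycle 2 start gives equal 60-day restricted means when wounds are independent (25.9 v 25.9 days with means 10/30), but tilts toward placebo under shared subject frailty of CV 0.7 (KB103 33.4 v placebo 35.8). Following past Cycle 2 start is therefore better than censoring there.

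**Step 3: Cycle 2 time to closure.** Mean days from Cycle 2 start:

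| Mean open/closed (days), shape, frailty | Placebo closed at start | KB103 | Placebo, closed counted as 0 | Placebo, open wounds only |
|---|---|---|---|---|
| 30/60, 1, none | 59% | 29.8 | 12.3 | 29.9 |
| 30/60, 2, none | 67% | 29.9 | 7.4 | 22.0 |
| 30/60, 1, wound CV 0.7 | 56% | 27.8 | 17.4 | 39.8 |
| 60/30, 1, wound CV 1.0 | 32% | 45.5 | 50.4 | 73.6 |

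Over all 11 scenarios, 31% to 86% of placebo wounds are already closed. Counting these as 0 days favours placebo in 10 of 11. Using open wounds only gives about no bias for the five exponential scenarios without frailty, favours placebo for shape 2, and favours KB103 with frailty or shape 0.5.

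**Step 4: is the healing rate shared within a subject?** I also took pairs with both wounds open at Cycle 2 start, the KB103 wound having closed within 13 weeks. Rates were lognormal (median healing 4 weeks, mean closed time 6 weeks, log-SD 0.5/1.0/1.5). If the two wounds of a subject have independent rates, median weeks to closure are 3.6 v 4.3, 2.8 v 5.4 and 2.1 v 7.3 (KB103 v placebo). If the rate is shared, each open wound has the same exponential remaining time, so the medians are equal (4.0 v 4.0, 4.1 v 4.1, 4.2 v 4.2). About 45% of placebo wounds are closed and so excluded here. Counted as 0 days, they bring the probability that KB103 closes first to 0.23 to 0.38.

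**The case against.** The strongest reply is that the SAP already avoids most of this. It has no per-cycle test. Its time to closure runs from first treatment, and its duration ends at the wound's own loss of closure, which continuing images can show. No text cuts placebo at Cycle 2 start. The protocol says only that the endpoints are evaluated or assessed after each cycle, and its objectives relative to placebo do not mention cycles. The formal Cochran-Mantel-Haenszel test is at weeks 8, 10 and 12.

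Much of this stands. The Cycle 1 duration bias is conditional on an analysis the documents permit but do not prescribe. What remains is that the protocol's per-cycle assessment has no rules and the SAP does not supply them. Its analysis of variance also says nothing about closures that have not ended.

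A reader might infer that the per-cycle comparisons favour KB103 even if it does nothing. The documents do not support that for Cycle 2. The direction depends on an unstated counting rule and on unknown heterogeneity. Protocol 1.6 does describe wide variation between recurring and long-open wounds, but Protocol 6.3 asks for similar wounds within a subject, so independent rates cannot be assumed. Nor are two primary objectives compromised throughout: Cycle 1 time to closure is unaffected, and Cycle 2 duration is followed by a fixed 3 months (Protocol 5.2), without the same truncation.

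**Conclusion.** The point holds in a limited form. The arms are not comparable at Cycle 2 start, so a Cycle 2 time-to-closure contrast with placebo is uninterpretable, with bias of undetermined sign. Cycle 1 duration is biased toward KB103 (placebo about 0.5 to 0.67 of KB103 under no effect) only if placebo closures are cut at Cycle 2 start and treated as complete. Followed to their own end, the null means agree.

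The sizes rest on assumed healing and closed times. They rest also on the 4.1 reading of the trigger; 5.5 leaves the arm open. The expansion trigger and any effect of gel or dressing were not modelled. With two KB103 areas, the one still closed when the other fails would be cut as well: in the simplest exponential case the placebo ratio is then (1/3)/(1/2) = 0.67.

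The practical weight is modest. Only 3 subjects are planned under version 4.0, and with 3 subjects even the worst handling of duration gives 3.5% to 8.7% rejection against a nominal 5%. It should be corrected, but it is below a must-fix.

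**What to change.** In Protocol 10.5.3 and SAP 8.1.2 to 8.1.3:

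1. Limit the KB103-versus-placebo comparison of time to closure to Cycle 1, counted from first treatment.
2. Measure Cycle 1 duration to each wound's own loss of closure, by the same SAP 8.1.3 criterion in both arms, using the images that continue past Cycle 2 start. Treat closures not ended at the last image as censored, in a paired time-to-event analysis. Days closed in a fixed window from first dose is an optional supplement.
3. Report Cycle 2 time to closure and duration descriptively, without a placebo test, and show how many placebo wounds were already closed when Cycle 2 began.
4. Reconcile Protocol 4.1 with 5.5 on which wound ends Observation Period 1.

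This is a change of wording and needs no new data. The cost is that Cycle 2 has no formal placebo comparison. One limitation remains: Protocol 4.1 applies product to the whole area, intact skin included, so a placebo closure followed into Cycle 2 may be partly observed under placebo gel and dressings. The report should say so.

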### 4.2 Sites and Trial Duration

One (1) investigative site is planned for this study.

The trial duration is variable depending on the duration of response following the first and second administration cycles. It is estimated that trial participants will be on study for 6 months to a year. Additional time for recruitment and screening is anticipated to take 1 month. Safety data is to be

collected by clinic visit or telephone contact approximately every 1 year for up to 5 years after the subject completes the final on-site or at-home visit as part of this protocol.

### **4.3 Concomitant Therapy and Skin Care**

Stanford is a major epidermolysis bullosa center and has an established multidisciplinary epidermolysis bullosa team. Subjects will have full access to the care provided by this team throughout participation in this study.

The Investigator is encouraged to restrict topical administration of any EB therapy to a wound that receives KB103 or placebo for a minimum of 72 hours following administration. Any therapy administered to the target wound should also be applied to the control wound. Throughout the study, any concomitant medications or treatments deemed necessary to provide adequate supportive care may be prescribed. In particular, medication should be considered during and after any biopsies to treat pain and/or anxiety (i.e. lidocaine, lorazepam, etc.). Routine skin care for DEB patients continues throughout the study. Though not anticipated due to the non-replicating nature of KB103, active herpes should be treated with an antiviral at the discretion of the Investigator.

Conscious sedation to anesthetize pain associated with biopsies is acceptable at the discretion of the Investigator.

### **4.4 Subject Enrollment and Withdrawal**

Written protocol and informed consent approval are required from the IRB prior to enrollment. Assent form approval is required from the IRB prior to enrolling subjects below the age of consent. All subjects or their respective legal guardians must personally sign and date the relevant consent and/or assent form before enrollment.

#### **4.4.1 Subject Identification and Number Assignment**

Subjects who sign the informed consent form are assigned a 3-digit subject identification number. Subject identification numbers begin with 001. This number identifies the subject throughout the study and must be used on all study documentation related to that subject.

#### **4.4.2 Withdrawal of Subjects**

A subject is free to withdraw from the study at any time for any reason without prejudice to their future medical care by the physician or at the institution. The Investigator or Sponsor may also withdraw the subject at any time in the interest of subject safety or for other reasons. Criteria for withdrawal include:

1. Consent/assent is withdrawn.
2. The subject refuses treatment and/or procedures/observations.
3. Occurrence of unmanageable adverse events or pregnancy.
4. For other reasons (e.g., significant protocol violation, non-compliance).

The Sponsor may be contacted if clarification is required. The primary reason for withdrawal must be recorded on the CRF. Comments or complaints made by the subject must also be recorded on the CRF. Withdrawal should be discussed with the medical monitor prior to withdrawal when possible. Subjects who wish to discontinue treatment or study procedures after receipt of KB103 are asked to continue in the Long-Term Follow-Up Period. Subjects who withdraw prior to the first KB103 administration are considered a screen failure and are replaced. The Sponsor reserves the right to terminate the study.

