**Table 1 - KB103-001 Stopping Criteria**

Event	Severity	Number of Events
A treatment emergent serious adverse event that is definitely or suspected to be related to KB103.	Any	1
An AE associated with HSV infection in combination with a positive RCV qPCR assay result.	Any	1
An immune response determined by the Investigator to be possibly, probably or definitely related to investigational product or a procedure.	Severe	1
Any treatment emergent systemic infection designated as possibly, probably or definitely related to investigational product or a procedure.	Moderate or higher	2 or more
A treatment emergent uncontrolled bacterial, viral, or fungal infection in an area administered investigational product where product sterility testing results reported post injection were positive for contamination.	Mild or higher	1

For subject safety, subjects should be followed in accordance with the study visits and procedures as outlined in the protocol. An occurrence of any of these safety observations is shared with the SMC and the appropriate authorities. The SMC reviews the results of the safety investigation and may request any additional data needed to assess the safety of restarting product administration. The SMC determines if the suspension can be lifted or if the trial terminates based on their review of the safety investigation.

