## 5.9 Long-Term Follow-Up Period

Upon completion of the End of Study / Early Termination Visit, subjects will enter into a Long-Term Follow-Up Period.

At a minimum, subjects will be contacted yearly for at least 5 years. Subjects will be contacted by phone. In addition, the subject's primary care provider will be asked to contact the Investigator regarding any unexpected or serious adverse events. Telephone contact reports will document the discussions and the information obtained will be captured on case report forms. The following activities will occur at the one-year follow-up intervals:

- Recording of exposures to mutagenic agents and other medicinal products
- Recording of any new serious adverse events, hospitalizations, or illnesses (including new malignancies, new incidence or exacerbation of a pre-existing neurologic disorder, new incidence or exacerbation of a prior rheumatologic or other autoimmune disorder, new incidence of a hematologic disorder).
- Discussion with primary care provider regarding medication and medical history.
- If a skin cancer occurs in the region of the KB103 administration, attempts will be made to collect samples of the skin cancer to evaluate cells for the presence of viral vector.

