## 9.4 Reporting Procedures

All adverse events occurring after KB103 administration observed by the investigator or reported by the subject (whether or not attributed to investigational product), are reported on the case report form.

Medically significant adverse events considered related to the investigational product by the investigator or the sponsor are followed until resolved or considered stable. The investigator must assign the following attributes: description; dates of onset and resolution; severity; assessment of relatedness to investigational product, and action taken. The investigator may be asked to provide follow-up information.

All deaths occurring on study must be reported to Krystal. These include deaths during the Long-Term Follow-Up period. For all deaths, available autopsy reports and relevant medical reports may be requested.

The investigator should notify the IRB of serious adverse events occurring at the site and other adverse event reports received from the sponsor, in accordance with local procedures.

It is left to the investigator’s clinical judgment whether or not an adverse event is of sufficient severity to require the subject’s removal from study. A subject may also voluntarily withdraw from study due to what he or she perceives as an intolerable adverse event. If either of these occurs, the subject is asked to undergo an early termination assessment and be given appropriate care under medical supervision until symptoms cease or the condition becomes stable. If the subject was permanently withdrawn from the study due to a serious adverse event, this information must be included in either the initial or follow-up Serious Adverse Event Report Form, and in the End of Study Case Report Form.

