6.3 Handling of Missing Data

Missing data will be handled as outlined below:

- All missing and partial dates for adverse events or for medications received after randomization will be queried for a value. If no value can be obtained, substitutions will be made as detailed in [Appendix 2](#). These substitutions will be used in calculations; however, the actual value recorded on the eCRF will be used in all listings.
- Missing primary endpoints, values after the last non-missing value would be replaced by the last recorded observed value. This is analogous to a last observation carried forward (LOCF) strategy for study discontinuations. For all the other endpoints, the missing values will not be imputed.
- The severity and causality assessment for adverse events cannot be missing. Missing data will be queried for a value.

7 Statistical Analysis Methods

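### Protocol 4.4.2 sends subjects who only stop study product by choice to follow-up without wound imaging, although SAP 7.1 expects week 8, 10 and 12 outcomes from them

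*Protocol*

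**What the plan says.** **Withdrawal rule.** Protocol 4.4.2 reads: "Subjects who wish to discontinue treatment or study procedures after receipt of KB103 are asked to continue in the Long-Term Follow-Up Period". The second withdrawal criterion in the same section also merges the two decisions: "The subject refuses treatment and/or procedures/observations".

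**What long-term follow-up is.** Protocol 5.9 places a visit before it: "Upon completion of the End of Study / Early Termination Visit, subjects will enter into a Long-Term Follow-Up Period". Contact is then at least yearly, and "Subjects will be contacted by phone". The listed activities are exposures, serious events, hospitalizations, illnesses, medication and medical history, and samples of any skin cancer in the treated region. Protocol 4.2 describes safety data "collected by clinic visit or telephone contact approximately every 1 year for up to 5 years". In the version 4.0 schedule (SAP Appendix 1, 11.1.4) the long-term follow-up column has no imaging entry.

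**What the SAP assumes.** SAP 7.1 reports early discontinuation of treatment separately from failure to complete the study. Its completer needs at least one administration of either treatment and attendance at weeks 8, 10 and 12; continued dosing is not required. SAP 8 states that efficacy is measured both on and off treatment.

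**Missing data.** SAP 8.1.1 bases the main analysis on observed ITT data, and 8.1.1.1 adds LOCF and per-protocol analyses. Time to closure and duration of closure (8.1.2, 8.1.3) are analysed on observed and LOCF data alike. SAP 6.3 describes the carry-forward rule: "This is analogous to a last observation carried forward (LOCF) strategy for study discontinuations".

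**The concern.** Stopping the product and leaving the study are different events. An ITT comparison at weeks 8, 10 and 12 needs outcomes after treatment stops, and the SAP's completer definition allows for that. Protocol 4.4.2 asks a subject who declines further dosing, but would still send phone images, to move to a period in which none are requested. The missing values are avoidable, and no later analysis can recover them.

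Neither planned analysis replaces the lost outcome. Observed ITT has no record for that subject at later weeks. LOCF assumes that the wound stays as last seen, yet the design expects wounds to re-open: Protocol 4.1 and 5.5 make re-opening or expansion the trigger for Cycle 2. A carried-forward closure could therefore outlast the real one. Duration of closure, a primary objective, is the most exposed.

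**Working it through.** The plan gives no sample-size, power or dropout figure to reproduce. The check compares the texts and then counts the loss per subject.

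**Step 1. Who is affected**

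| Reason dosing stops | What the protocol asks next | Imaging continues? |
|---|---|---|
| Wound closure or 3 months (5.5, 5.7) | Observation period, home images every 2 to 3 days | Yes |
| Suspension under the stopping criteria (5.1) | "subjects should be followed in accordance with the study visits and procedures as outlined in the protocol" | Yes |
| Removal or withdrawal for an adverse event (9.4) | "the subject is asked to undergo an early termination assessment" | One assessment, contents not listed |
| Subject wishes to stop treatment only (4.4.2) | Long-term follow-up, after the visit in 5.9 | Not requested |
| Subject wishes to stop procedures (4.4.2) | Long-term follow-up, after the visit in 5.9 | Not requested |

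The gap is the fourth row. Such a subject is handled like the fifth row, although SAP 7.1 would still accept the subject as a completer.

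**Step 2. Size in the version 4.0 cohort**

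Inputs: 3 subjects (Protocol synopsis, 4.1); 3 analysis weeks (SAP 8.1.1); one placebo area and one or two KB103 areas per subject (Protocol 6.3).

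- Paired subject-week records: 3 × 3 = 9.
- One subject stops before week 8: 3 of 9 = 33%.
- Stops between weeks 8 and 10: 2 of 9 = 22%. Stops between weeks 10 and 12: 1 of 9 = 11%.
- Counted by area: if the stopper has two areas and the others three, 6 / (6 + 9 + 9) = 6/24 = 25%. If the stopper has three and the others two, 9 / (9 + 6 + 6) = 9/21 = 43%.

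**Step 3. What carrying forward can do (illustration)**

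Take one KB103 and one placebo wound per subject. Assume a healed-proportion difference *d* = 0.50 in the two retained subjects. Let *x* be the stopper's carried-forward difference: −1 if only placebo is healed, 0 if the wounds agree, +1 if only KB103 is healed. The LOCF difference is (2*d* + *x*)/3:

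- *x* = −1: (1 − 1)/3 = 0
- *x* = 0: (1 + 0)/3 = 0.33
- *x* = +1: (1 + 1)/3 = 0.67

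The observed-data difference stays at 0.50. The carried-forward pair decides where in 0 to 0.67 the LOCF result falls.

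**Step 4. The paired t-test in Protocol 10.5.3**

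At a fixed week with observed data, going from 3 pairs to 2 raises the one-sided 5% critical value from 2.920 (df 2) to 6.314 (df 1). This does not apply to the treatment endpoint in Protocol 10.7, which uses the last available measurement and so keeps the pair, on an earlier value.

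**Step 5. In the pooled analysis**

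One version 4.0 stopper is 3 of 36 subject-week records (8.3%) with the 12 subjects in SAP 4.1, or 3 of 42 (7.1%) with the 14 in the Protocol synopsis. Both totals assume that every subject has records at all three weeks. The version 1.0 schedule has no week 8 or week 10 visit, so the true totals are smaller.

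**The case against.** The strongest reply is that nothing in 4.4.2 forbids imaging. Table 2, footnote 4, has home imaging continuing throughout the study at bandage changes, so it is not tied to dosing. Protocol 5.8 allows unscheduled visits with any monthly-visit procedure. With SAP 7.1 already separating the two states, the sponsor could say that the intent is clear and only the wording is loose. It is fair that imaging is not prohibited. But the only request addressed to a subject who stops by choice is to enter a period whose schedule column has no imaging, and unscheduled visits are optional. The SAP cannot analyse data that the protocol does not ask for.

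Several stronger readings are tempting and are not supported:

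- **That the whole ITT result rests on missing or carried-forward values.** Only the stopper's later values are affected. ITT membership needs one paired post-administration assessment, so earlier data stay in. For the healing proportion, LOCF is a sensitivity analysis.
- **That subjects pass directly to telephone contact.** An End of Study / Early Termination visit comes first. Its procedures are not listed, and one visit cannot supply later weeks.
- **That the same rule governed all cohorts.** The withdrawal text of versions 1.0 to 3.2 is not in the documents, so the exposure cannot be spread over every wound in the SAP table.
- **That stopping is known to follow poor healing.** The documents report no discontinuations or reasons for them. Protocol 1.6 points the other way: caregivers asked for more administrations to wounds that had benefited but not closed.

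**Conclusion.** The point holds in limited form. Protocol 4.4.2 does not separate voluntarily stopping product from refusing procedures, and it conflicts with SAP 7.1, which does. If the protocol is followed as written, a subject who chooses to stop before week 8 provides no wound areas at weeks 8, 10 and 12, although the SAP would have counted and used them.

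The size is 33% of paired subject-week records in the version 4.0 cohort per such subject (25% to 43% counted by area), and roughly 7% to 8% of the pooled records under the totals in step 5. This rests on two assumptions: that at least one subject stops by choice before week 8, for which the documents give no rate; and that version 4.0 outcomes at those weeks come from the routine images and visits, since that schedule has no visits fixed at weeks 8, 10 and 12.

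Priority is minor to moderate. This is a pilot without a formal sample size, and the amendment reaches only about three subjects. The change is worth making because it costs little and the data cannot be recovered afterwards.

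**What to change.** **Protocol 4.4.2.** Split the sentence. Ask subjects who stop product but do not refuse procedures to continue the existing home imaging at its usual frequency through week 12, with any remaining visits they accept, and then to enter long-term follow-up. Only those who refuse procedures move there after the Early Termination visit. Reword withdrawal criterion 2 so that declining treatment alone is not withdrawal from the study.

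**SAP 6.3 and 8.1.1.** State that images taken after treatment stops are included in the main ITT analysis, and that carry-forward applies only where no image exists.

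This concerns data collection only and does not touch the decision to stop treatment.

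**Cost.** A short protocol edit with a matching consent-form line, and one or two SAP sentences. The imaging app and bandage-change routine already exist (Protocol 7.1.1). The downside is a small extra effort for subjects who have stopped, who remain free to decline.
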